## 7.6. Treatment Compliance

The investigational product will be administered at the clinical site, and documentation of treatment administration will occur at the site.

## 7.7. Concomitant Therapy

The use of medications for stable medical conditions that are not excluded per the protocol inclusion/exclusion criteria is allowed, at the investigator's discretion, and following approval by the clinical pharmacologist/clinical research physician (CRP), or designee. Those medications that impact gastric motility should be avoided. The use of medications and/or procedures for acute treatment of migraine or other pain or injury is allowed, with some limitations. The migraine attack that defines Period 1, Day 1 should not be treated with any medication, including, but not limited to, triptans, ergotamines, or analgesic medications. All other migraine attacks occurring during the study may be treated according to the following limitations: triptans and ergotamines should be used within labeled recommendations (and not to exceed 9 days per month in total); acetaminophen, aspirin, and nonsteroidal anti-inflammatory drugs are allowed on headache days and for minor ailments (not to exceed 14 days per month in total). Triptans, ergotamines, and analgesics should be avoided for 24 hours prior to dosing in Period 2. Any medications or procedures to prevent migraine (including, but not limited to, propranolol and topiramate) are not allowed within 30 days prior to the first dose and until the follow-up visit.

Patients will be instructed to consult with the investigator or study coordinator at the site before taking any new prescribed medications, over-the-counter medications, or supplements. If the need for other concomitant medication arises, inclusion or continuation of the patient may be at the discretion of the investigator after consultation with a Lilly clinical pharmacologist, CRP, or designee. Any medication used during the course of the study must be documented.

## 7.8. Treatment after the End of the Study

Lasmiditan will not be made available to patients after the end of the study.

#### 8. Discontinuation Criteria

Patients discontinuing from the study prematurely for any reason must complete AE and follow-up procedures per Section 2 of this protocol.

## 8.1. Discontinuation from Study Treatment

Discontinuation of the investigational product for abnormal liver tests **should be considered** by the investigator when a patient meets 1 of the following conditions after consultation with the Lilly designated medical monitor:

- ALT (alanine aminotransferase) or AST (aspartate aminotransferase) > 8× upper limit of normal (ULN)
- ALT or AST >5× ULN sustained for more than 2 weeks or
- ALT or AST >3× ULN and total bilirubin level >2× ULN or International Normalized Ratio (INR) >1.5 or
- ALT or AST >3× ULN with the appearance of fatigue, nausea, vomiting, right upper quadrant pain or tenderness, fever, rash, and/or eosinophilia (>5%)
- ALP (alkaline phosphatase) >3× ULN
- ALP >2.5× ULN and total bilirubin >2× ULN
- ALP >2.5× ULN with the appearance of fatigue, nausea, vomiting, right quadrant pain or tenderness, fever, rash, and/or eosinophilia (>5%).

## 8.1.1. Discontinuation of Inadvertently Enrolled Patients

If the sponsor or investigator identifies a patient who did not meet enrollment criteria and was inadvertently enrolled, a discussion must occur between the Lilly clinical pharmacologist/CRP or designee and the investigator to determine if the patient may continue in the study. If both agree it is medically appropriate to continue, the investigator must obtain documented approval from the Lilly clinical pharmacologist/CRP or designee to allow the inadvertently enrolled patient to continue in the study with or without continued treatment with investigational product.

## 8.2. Discontinuation from the Study

Patients will be discontinued in the following circumstances:

- Enrollment in any other clinical study involving an investigational product or enrollment in any other type of medical research judged not to be scientifically or medically compatible with this study
- Participation in the study needs to be stopped for medical, safety, regulatory, or other reasons consistent with applicable laws, regulations, and good clinical practice (GCP)
- Investigator Decision
  - o the investigator decides that the patient should be discontinued from the study

o if the patient, for any reason, requires treatment with another therapeutic agent that has been demonstrated to be effective for treatment of the study indication, discontinuation from the study occurs prior to introduction of the new agent

#### • Patient Decision

o the patient, or legal representative, requests to be withdrawn from the study.

## 8.3. Patients Lost to Follow-Up

A patient will be considered lost to follow-up if he or she fails to return for a scheduled visit and is unable to be contacted by the study site. Site personnel are expected to make diligent attempts to contact patients who fail to return for a scheduled visit or were otherwise unable to be followed up by the site.

# 9. Study Assessments and Procedures

Section 2 lists the Schedule of Activities, detailing the study procedures and their timing (including tolerance limits for timing).

Appendix 2 lists the laboratory tests that will be performed for this study.

Appendix 5 provides a summary of the maximum number and volume of invasive samples, for all sampling, during the study.

Unless otherwise stated in subsections below, all samples collected for specified laboratory tests will be destroyed within 60 days of receipt of confirmed test results. Certain samples may be retained for a longer period, if necessary, to comply with applicable laws, regulations, or laboratory certification standards.

## 9.1. Efficacy Assessments

This section is not applicable for this study.

#### 9.2. Adverse Events

Investigators are responsible for monitoring the safety of patients who have entered this study and for alerting Lilly or its designee to any event that seems unusual, even if this event may be considered an unanticipated benefit to the patient.

The investigator is responsible for the appropriate medical care of patients during the study.

Investigators must document their review of each laboratory safety report.

The investigator remains responsible for following, through an appropriate health care option, AEs that are serious or otherwise medically important, considered related to the investigational product or the study, or that caused the patient to discontinue the investigational product before completing the study. The patient should be followed until the event resolves, stabilizes with appropriate diagnostic evaluation, or is reasonably explained. The frequency of follow-up evaluations of the AE is left to the discretion of the investigator.

After the ICF is signed, study site personnel will record, via the eCRF, the occurrence and nature of each patient's preexisting conditions, including clinically significant signs and symptoms of the disease under treatment in the study. Additionally, site personnel will record any change in the condition(s) and the occurrence and nature of any AEs.

The investigator will interpret and document whether or not an AE has a reasonable possibility of being related to study treatment or a study procedure, taking into account the disease, concomitant treatment or pathologies.

A "reasonable possibility" means that there is a potential cause and effect relationship between the investigational product and/or study procedure and the AE.

Planned surgeries should not be reported as AEs unless the underlying medical condition has worsened during the course of the study.

#### 9.2.1. Serious Adverse Events

An SAE is any AE from this study that results in one of the following:

- death
- initial or prolonged inpatient hospitalization
- a life-threatening experience (that is, immediate risk of dying)
- persistent or significant disability/incapacity
- congenital anomaly/birth defect
- important medical events that may not be immediately life-threatening or result in death or hospitalization but may jeopardize the patient or may require intervention to prevent one of the other outcomes listed in the definition above.

Study site personnel must alert the Lilly CRP/clinical pharmacologist, or its designee, of any SAE as soon as practically possible.

Additionally, study site personnel must alert Lilly Global Patient Safety, or its designee, of any SAE within 24 hours of investigator awareness of the event via a sponsor-approved method. If alerts are issued via telephone, they are to be immediately followed with official notification on study-specific SAE forms. This 24-hour notification requirement refers to the initial SAE information and all follow-up SAE information.

Although all AEs are recorded in the eCRF after signing informed consent, SAE reporting to the sponsor begins after the patient has signed informed consent and has received investigational product. However, if an SAE occurs after signing informed consent, but prior to receiving investigational product, AND is considered reasonably possibly related to a study procedure then it MUST be reported.

Investigators are not obligated to actively seek AEs or SAEs in patients once they have discontinued from and/or completed the study (the patient summary eCRF has been completed). However, if the investigator learns of any SAE, including a death, at any time after a patient has been discharged from the study, and he/she considers the event reasonably possibly related to the study treatment or study participation, the investigator must promptly notify Lilly.

Pregnancy (maternal or paternal exposure to investigational product) does not meet the definition of an AE. However, to fulfill regulatory requirements any pregnancy should be reported following the SAE process to collect data on the outcome for both mother and fetus.

#### 9.2.1.1. Suspected Unexpected Serious Adverse Reactions

Suspected unexpected serious adverse reactions (SUSARs) are serious events that are not listed in the IB and that the investigator reports as related to investigational product or procedure. Lilly has procedures that will be followed for the recording and expedited reporting of SUSARs that are consistent with global regulations and the associated detailed guidances.

#### 9.2.2. Complaint Handling

Lilly collects product complaints on investigational products and drug delivery systems used in clinical trials in order to ensure the safety of study participants, monitor quality, and to facilitate process and product improvements.

Patients should be instructed to contact the investigator as soon as possible if he or she has a complaint or problem with the investigational product so that the situation can be assessed.

#### 9.3. Treatment of Overdose

For the purposes of this study, an overdose of lasmiditan is considered any dose higher than the planned study dose. There is no specific antidote for lasmiditan. In the event of overdose, the patient should receive appropriate supportive care and AEs should be documented.

No drug interaction studies in humans have yet been performed with lasmiditan.

## 9.4. Safety

#### 9.4.1. Laboratory Tests

For each patient, laboratory tests detailed in Appendix 2 should be conducted according to the Schedule of Activities (Section 2).

Lilly or its designee will provide the investigator with the results of laboratory tests analyzed by a central vendor.

## 9.4.2. Vital Signs

For each patient, vital signs measurements should be conducted according to the Schedule of Activities (Section 2) and following the study-specific recommendations included in the Manual of Operations for the study.

Blood pressure and pulse rate should be measured after at least 5 minutes supine. All supine blood pressure and pulse rate measurements except for screening will be done in triplicate at approximately 1-minute intervals. The last triplicate vital sign can be used as the supine vital sign for the calculation of orthostatic changes.

Where orthostatic measurements are required, patients should be supine for at least 5 minutes and stand for at least 2 minutes.

If the patient feels unable to stand, supine vital signs only will be recorded.

Unscheduled orthostatic vital signs should be assessed, if possible, during any AE of dizziness or posture-induced symptoms. Additional vital signs may be measured during each study period if warranted.

## 9.4.3. Electrocardiograms

For each patient, ECGs should be collected according to the Schedule of Activities (Section 2) and the study-specific recommendations included in the Manual of Operations for the study.

Any clinically significant findings from ECGs that result in a diagnosis and that occur after the patient receives the first dose of the investigational product should be reported to Lilly, or its designee, as an AE via the eCRF.

For each patient, a single 12-lead digital ECG will be collected according to the Schedule of Activities. Electrocardiograms must be recorded before collecting any blood samples. Patients must be supine for approximately 5 to 10 minutes before ECG collection and remain supine but awake during ECG collection. Electrocardiograms may be obtained at additional times, when deemed clinically necessary. All ECGs recorded should be stored at the investigational site.

Electrocardiograms will be interpreted by a qualified physician (the investigator or qualified designee) at the site as soon after the time of ECG collection as possible, and ideally while the patient is still present, to determine whether the patient meets entry criteria at the relevant visit(s) and for immediate patient management, should any clinically relevant findings be identified.

If a clinically significant finding is identified (including, but not limited to, changes in QT/QTc interval from baseline) after enrollment, the investigator will determine if the patient can continue in the study. The investigator, or qualified designee, is responsible for determining if any change in patient management is needed, and must document his/her review of the ECG printed at the time of collection. Any new clinically relevant finding should be reported as an AE.

## 9.4.4. Colombia Suicide Severity Rating Scale

Any occurrence of suicide-related thoughts and behaviors will be assessed as indicated in the Schedule of Activities (Section 2) using the Columbia Suicide Severity Rating Scale (C-SSRS). The C-SSRS is administered by an appropriately trained healthcare professional with at least 1 year of patient care/clinical experience.

The nonleading AE collection should occur prior to the collection of the C-SSRS. If a suicide-related event is discovered during the C-SSRS, but was not captured during the nonleading AE collection, sites should not change the AE form. If an event is serious or leads to discontinuation, this is an exception where the SAE and/or AE leading to discontinuation should be included on the AE form and the process for reporting SAEs should be followed.

Terms captured by the use of the C-SSRS can be mapped to Columbia Classification Algorithm for Suicide Assessment (Posner et al. 2007) to facilitate future pooling of data.

The first time the scale is administered in this study, the C-SSRS "Baseline" version will be used, and the findings will constitute the baseline assessment. The C-SSRS "Since Last Visit" scale will be used for all subsequent assessments. If a suicide-related thought or behavior is identified at any time during the study, a thorough evaluation will be performed by a study physician, and appropriate medical care will be provided. It is recommended that a patient be assessed by a psychiatrist or appropriately trained professional to assist in deciding whether the patient should be discontinued from study treatment. A patient does not necessarily have to be discontinued if they have self-injurious behavior that would be classified as non-suicidal

self-injurious behavior. Of course, if this situation arises, it is recommended that the patient be referred to a psychiatrist or appropriately trained professional.

The Lilly Self-Harm Supplement should be completed every time the C-SSRS is administered. If there are positive findings on the Self-Harm Supplement, then the Lilly Self-Harm Follow-Up form will be used to collect additional information to allow for a more complete assessment of these behaviors.

## 9.4.5. Safety Monitoring

The Lilly clinical pharmacologist or CRP/scientist will monitor safety data throughout the course of the study.

Lilly will review SAEs within time frames mandated by company procedures. The Lilly clinical pharmacologist or CRP will periodically review the following data:

- trends in safety data
- laboratory analytes
- AEs

When appropriate, the Lilly clinical pharmacologist or CRP will consult with the functionally independent Global Patient Safety therapeutic area physician or clinical research scientist.

#### 9.4.5.1. Hepatic Safety

If a study patient experiences elevated ALT  $\geq$ 3× ULN, ALP  $\geq$ 2× ULN, or elevated total bilirubin  $\geq$ 2× ULN, liver tests (Appendix 4) should be repeated within 3 to 5 days including ALT, AST, ALP, total bilirubin level, direct bilirubin, gamma-glutamyl transferase (GGT), and creatine kinase to confirm the abnormality and to determine if it is increasing or decreasing. If the abnormality persists or worsens, clinical and laboratory monitoring should be initiated by the investigator based on consultation with the Lilly clinical pharmacologist or CRP. Monitoring should continue until levels normalize and/or are returning to approximate baseline levels.

Additional safety data should be collected if 1 or more of the following conditions occur:

- elevation of serum ALT to  $\geq 5 \times$  ULN on 2 or more consecutive blood tests
- elevated serum total bilirubin level to  $\geq 2 \times$  ULN (except for cases of known Gilbert's syndrome)
- elevation of serum ALP to  $\geq 2 \times$  ULN on 2 or more consecutive blood tests
- patient discontinued from treatment due to a hepatic event or abnormality of liver tests
- hepatic event considered to be an SAE.

#### 9.5. Pharmacokinetics

At the visits and times specified in the Schedule of Activities, venous blood samples of approximately 2 mL each will be collected to determine the plasma concentrations of lasmiditan

and its 5 major metabolites. A maximum of 3 samples may be collected at additional time points during each study period if warranted and agreed upon between both the investigator and sponsor. Instructions for the collection and handling of blood samples will be provided by the sponsor. The actual date and time (24-hour clock time) of each sampling will be recorded.

#### 9.5.1. Bioanalysis

Samples will be analyzed at a laboratory approved by the sponsor and stored at a facility designated by the sponsor.

Concentrations of lasmiditan and its 5 major metabolites will be measured using a validated LC-MS/MS method.

Plasma remaining after the analyses may be used for exploratory work to further understand the disposition and metabolism of lasmiditan or the probe substrates.

Bioanalytical samples collected to measure investigational product concentrations will be retained for a maximum of 1 year following last patient visit for the study.

## 9.6. Pharmacodynamics

This section is not applicable for this study.

#### 9.7. Genetics

A blood sample will be collected for pharmacogenetic analysis as specified in the Schedule of Activities, where local regulations allow.

Samples will not be used to conduct unspecified disease or population genetic research either now or in the future. Samples will be used to investigate variable exposure or response to lasmiditan and to investigate genetic variants thought to play a role in migraine. Assessment of variable response may include evaluation of AEs or differences in efficacy.

All samples will be coded with the patient number. These samples and any data generated can be linked back to the patient only by the investigative site personnel.

Samples will be retained for a maximum of 15 years after the last patient visit, or for a shorter period if local regulations and/or ERBs impose shorter time limits, for the study at a facility selected by Lilly or its designee. This retention period enables use of new technologies, response to regulatory questions, and investigation of variable response that may not be observed until later in the development of lasmiditan or after lasmiditan is commercially available.

Molecular technologies are expected to improve during the 15 year storage period and therefore cannot be specifically named. However, existing approaches include whole genome or exome sequencing, genome wide association studies, multiplex assays, and candidate gene studies. Regardless of technology utilized, data generated will be used only for the specific research scope described in this section.

#### 9.8. Biomarkers

Biomarker research is performed to address questions of relevance to drug disposition, target engagement, pharmacodynamics, mechanism of action, variability of patient response (including safety), and clinical outcome. Sample collection is incorporated into clinical studies to enable examination of these questions through measurement of biomolecules including DNA, RNA, proteins, lipids, and other cellular elements.

Blood samples for non-pharmacogenetic biomarker research will be collected at the times specified in the Schedule of Activities (Section 2), where local regulations allow. Biomarkers assayed may include CCI and CCI, as well as additional biomarkers that may be of interest in future diagnostics/treatments of neurological conditions.

Samples will be used for research on the drug target, disease process, variable response to lasmiditan, pathways associated with migraine, mechanism of action of lasmiditan, and/or research method, or for validating diagnostic tools or assay(s) related to migraine.

All samples will be coded with the subject number. These samples and any data generated can be linked back to the patient only by the investigative site personnel.

Samples will be retained for a maximum of 15 years after the last patient visit, or for a shorter period if local regulations and/or ERBs impose shorter time limits, at a facility selected by Lilly or its designee. This retention period enables use of new technologies, response to regulatory questions, and investigation of variable response that may not be observed until later in the development of lasmiditan or after lasmiditan is commercially available.

#### 9.9. Health Economics

This section is not applicable for this study.

# 10. Statistical Considerations and Data Analysis

### 10.1. Sample Size Determination

Approximately 20 patients may be enrolled to ensure 12 patients with adequate PK data complete the study. Patients who do not complete both periods of the study may be replaced.

For AUC or  $C_{max}$ , assuming inter-patient CV% of 40% (based on previous studies) and a sample size of 12, the 90% confidence interval around the geometric mean of the within-patient ratios (migraine/inter-ictal) will have a half-width of 20.1% with 90% coverage probability.

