#### 10.3.2.2. Pharmacokinetic Statistical Inference

Pharmacokinetic parameter estimates will be evaluated to determine the impact of changes in gastric motility that may accompany acute migraine attacks on the PK of lasmiditan and its metabolites. Log-transformed  $C_{max}$ ,  $AUC(0\text{-}t_{last})$ , and  $AUC(0\text{-}\infty)$  parameters will be evaluated in a linear mixed-effects model with a fixed effect for period (ie, migraine status; lasmiditan administered during a migraine versus lasmiditan administered during the inter-ictal period) and a random effect for patient. The treatment differences will be back transformed to present the ratios of geometric means and the corresponding 90% confidence interval.

The tmax will be analyzed using a Wilcoxon signed rank test. Estimates of the median difference based on the observed medians, 90% confidence intervals, and the p-value from the Wilcoxon test will be calculated.

Additional analysis may be performed if warranted upon review of the data.

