9.3.2 Pharmacokinetic Statistical Methodology

Pharmacokinetic parameter estimates will be evaluated to determine the impact of changes in gastric motility that may accompany acute migraine attacks on the PK of lasmiditan and its metabolites. All plasma concentration data and derived PK parameters will be summarized by period (i.e., migraine status; lasmiditan administered during a migraine versus lasmiditan administered during the inter-ictal period).

Log-transformed C_{max} , AUC(0-tlast), and AUC(0-∞) parameters will be evaluated in a linear mixed-effects model with a fixed effect for period (ie, migraine status; lasmiditan administered during a migraine versus lasmiditan administered during the inter-ictal period) and a random effect for patient. The treatment period differences will be back transformed to present the ratios of geometric means and the corresponding 90% confidence interval.

An example of the SAS code that will be used is as follows:

```
proc mixed data=xxxx;
class period subjid;
model l_pk = period / alpha=0.1;
random subjid;
lsmeans period / pdiff;
run;
```

where l_pk is the log-transformed (base e) PK parameter.

The t_{max} will be analyzed using a Wilcoxon signed rank test. Estimates of the median difference based on the observed medians, 90% confidence intervals, and the p-value from the Wilcoxon test will be calculated.

Additional analysis may be performed if warranted upon review of the data. Insert stats methodology here.

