11. CHANGES FROM THE PROTOCOL SPECIFIED STATISTICAL ANALYSES

There were no changes from the protocol specified statistical analyses.

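### The 20.1% half-width behind n = 12 carries an undefined 90% probability: read as assurance the design does not have it, and read as confidence level one symmetric figure misdescribes a ratio interval

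*Protocol*

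**What the plan says.** Protocol 10.1 sets the size of the study: "Approximately 20 patients may be enrolled to ensure 12 patients with adequate PK data complete the study". The precision claim follows, "assuming inter-patient CV% of 40% (based on previous studies) and a sample size of 12": it concerns "the 90% confidence interval around the geometric mean of the within-patient ratios (migraine/inter-ictal") and says that this interval "will have a half-width of 20.1% with 90% coverage probability". SAP 7 repeats the claim with the same figures. Neither document gives the formula, the quantile, the scale on which half-width is measured, or a definition of coverage probability.

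The interval to be reported is described elsewhere. Log-transformed Cmax and AUC are "evaluated in a linear mixed-effects model with a fixed effect for period" (SAP 9.3.2). Protocol 10.3.2.2 adds "a random effect for patient. The treatment differences will be back transformed to present the ratios of geometric means and the corresponding 90% confidence interval". In SAP 9.3.2 the example SAS code contains "model l_pk = period / alpha=0.1" with patient as a random effect, so the variance is estimated from the data. SAP 11 confirms the analysis: "There were no changes from the protocol specified statistical analyses".

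**The concern.** This is the only precision statement in either document and the only numerical support for 12 completers. With 12 patients and an estimated variance, the width of the interval is itself random, yet the sentence says what the interval will have and attaches a 90% probability. The words *90% confidence interval* already fix the level, so the added phrase is non-redundant only if it means the chance of achieving the stated width. Read that way, it promises a property that has to be checked. Read the other way, it leaves one symmetric percentage for an interval that is asymmetric once back-transformed.

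At stake is whether a reader of the protocol or the study report is told correctly how precise the primary comparison was planned to be. The analysis itself is not in question.

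**Working it through.** **Inputs**
- CV 40% and n = 12 (Protocol 10.1, SAP 7).
- Log-scale SD = sqrt(ln(1 + 0.40²)) = 0.3853. Using it as the SD of the within-patient log-ratio is an assumption: the documents call the 40% an inter-patient CV.
- SE = 0.3853/sqrt(12) = 0.1112.
- Normal quantile z(0.95) = 1.6449.
- The planned mixed model with 12 complete pairs gives 24 observations less model rank 13, that is 11 df, and t(0.95, 11) = 1.7959.

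**Step 1. Reproduce 20.1%.** Two calculations do so.
- *Normal quantile, upper arm:* exp(1.6449 × 0.1112) − 1 = exp(0.1829) − 1 = 20.07%.
- *t on 11 df, average of the arms at a ratio of 1:* the log half-width is 1.7959 × 0.1112 = 0.1997. The limits are exp(0.1997) = 1.2211 and exp(−0.1997) = 0.8190, and (1.2211 − 0.8190)/2 = 20.11%.

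Both round to 20.1%, and the documents do not say which was used. Both plug in the assumed SD; neither allows for sampling variation in the estimated SD.

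**Step 2. Chance of achieving 20.1%.** The realised log half-width is 1.7959 × s/sqrt(12), where 11s²/0.3853² is chi-square on 11 df. For a target w on the log scale, P = P(chi-square(11) ≤ 11 × (w/0.1997)²).

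| How half-width is measured | w | Probability |
|---|---|---|
| Upper arm | ln(1.201) = 0.1832 | 0.40 |
| Average of arms | asinh(0.201) = 0.1997 | 0.56 |
| Log scale | 0.201 | 0.57 |
| Lower arm | −ln(1 − 0.201) = 0.2244 | 0.76 |

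One million simulated trials gave 0.401 for the upper arm. No scale reaches 0.90.

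**Step 3. Half-width met with 90% probability at n = 12.** The inflation factor is sqrt(chi-square(0.90, 11)/11) = sqrt(17.275/11) = 1.2532. The log half-width becomes 0.1997 × 1.2532 = 0.2503.
- Upper arm: exp(0.2503) − 1 = 28.4%.
- Average of arms: sinh(0.2503) = 25.3%.

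**Step 4. Completers needed for 20.1% with 90% probability.** By the formula of step 2 with n varied:
- Upper arm: 20 completers (19 give 0.893, 20 give 0.930).
- Average of arms: 17.

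**Step 5. If the phrase only repeats the confidence level.** With the observed SD equal to the assumed SD, the arms are exp(0.1997) − 1 = +22.1% and 1 − exp(−0.1997) = 18.1% downwards. An upper limit of 1.201 at an estimated ratio of 1, which a single 20.1% suggests, would be 1.221 under the planned model.

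**The case against.** The strongest reply is that coverage probability ordinarily means the confidence level of an interval. On that reading the documents give no guarantee, and the probabilities in steps 2 to 4 contradict nothing. This stands as a possible reading. The fact that 20.1% is reproduced without any assurance step even supports it. It does not rescue the sentence, because the phrase is then redundant and the single percentage still hides two unequal arms.

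A reader might infer that the planners used the normal quantile by mistake and that 20.1% should simply read 22.1%. The documents do not support that. Half the back-transformed width of the planned t interval is also 20.1%, so on a literal reading of half-width there is no quantile error. A reader might also infer that the plan promises 90% and delivers 40%. That joins one reading of the phrase to the least favourable scale; the other scales give 0.56, 0.57 and 0.76.

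Three further points limit the consequence.
- About 20 patients may be enrolled and non-completers may be replaced. With 14 completers the t-based upper arm is 20.0%, and with 20 it is 16.1%. The shortfall belongs to the floor of 12, not to the trial as a whole.
- Every figure depends on the SD. With equal variances, 0.385 for the log-ratio corresponds to a within-patient correlation of 0.5. At an assumed 0.6 the upper arm at n = 12 is 19.6%, at 0.7 it is 16.7%, and below 0.5 it exceeds 22.1%. The documents give no correlation.
- The aim is estimation. No margin, power statement or decision rule rests on 20.1%, and the reported interval will show the precision achieved.

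**Conclusion.** The point holds as a defect in the precision statement, at the lower end of what should be corrected. Given an SD of 0.385 for the within-patient log-ratio, 12 complete pairs and the planned t-based interval, a 90% chance of a 20.1% half-width is not a property of the design on any scale (0.40 to 0.76). If no such chance was meant, the sentence still gives one symmetric number for an interval of about -18.1%/+22.1%.

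The documents settle neither the intended meaning nor the origin of 20.1%. The conclusion does not depend on either. It is not a finding that 12 completers are too few or that the planned model is wrong. Whether an inter-patient CV is the right input is a separate question; the t and chi-square factors apply on the log scale whatever SD is used.

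**What to change.** Keep n = 12. In Protocol 10.1 and SAP 7, delete the reference to coverage probability and replace the precision sentence with:

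> With 12 completers, and assuming the SD of the within-patient log-ratio is 0.385 (corresponding to a CV of 40%; an assumption, because the 40% is quoted as an inter-patient CV), if the observed SD equals the assumed SD the 90% CI (t, 11 df) is the estimated ratio divided and multiplied by 1.22 (-18.1%/+22.1%); with 90% probability the factor will not exceed 1.28.

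This wording is correct whichever calculation produced 20.1%. The 1.22 is a plug-in value and should not be called expected: the median upper arm is 21.4%, not 22.1%. If the SD assumption changes, recompute with the same t and chi-square factors.

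The cost is one sentence in each document. No patients are added and the analysis is unchanged. The downside is a slightly less favourable stated precision.
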